In routine care in this setting, viral load tests are to be repeated every three months in pregnancy and every six months during breastfeeding, so we expect that most women will have a routine viral load completed before six months postpartum. To avoid additional blood draws for the participant, at the follow-up visit, the study staff will check NHLS to determine the most recent viral load test. If the participant has had no viral load test within 3 months prior to the six-month study follow-up visit, a blood draw for viral load will be conducted by the clinical staff at the Gugulethu CHC. A clinic nurse will collect 5 ml of venous blood, which will be transported daily to the National Health Laboratory Services (NHLs) for HIV viral load testing (Abbott Molecular RealTime HIV-1 assay (Abbott Molecular, Illinois, USA). We will not recontact participants about viral load results unless participants are on ART and the viral load result indicates lack of viral suppression. In that case, results will be made available to participants over the phone (or in person, at participant's wish) with appropriate referrals. For all participants, viral load results will be captured using the participants provincial folder number into the NHLs database, as is standard practice for routine laboratory results in South Africa.

Uninstall app

During the follow-up visit, the CareConekta app will be uninstalled from each participant's phone.

Reimbursement

After all the above steps are complete, the enrollment visit will conclude with providing the participant R150 reimbursement for transport and missed opportunity costs. Payment will be made in cash and/or grocery vouchers and will be recorded in a reimbursement log.

File review activities

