Electronic and paper files will be reviewed after the participant's final visit to assess engagement in HIV care. If the participant fails to return for a final visit, files will be reviewed a minimum of seven months after estimated delivery. Electronic data on health facility visits and pharmacy dispensing, including facility recorded deaths, will be requested the Provincial Health Data Centre of the Western Cape Department of Health by providing a list of folder numbers of women who have consented and enrolled in the study. These data include all public health facilities in the Western Cape Province, which is the location of the study site. Laboratory records, including viral loads, from any South African facility will be abstracted from the NHLS database. Participants in both arms who are lost from the study at the time of study close will be traced through staff outreach and electronic/paper medical records. Informed consent will include permission to link with electronic medical records.

Table of schedule of measures

Item for completion	Enrolment	Early postpartum phone call	6 months postpartum
Eligibility Checklist	x		
Informed Consent	x		
Linkage form	x	x child details	
Randomisation log	x		
Demographics and medical history	x		x
Maternal mobility (past and planned)	x		x
Maternal clinic switching	x		x
Perceived barriers and facilitators of engagement in care	x		x
Depression (PHQ-4)	x		x
Alcohol and drug use (AUDIT-C and DUDIT Q1)	x		x
Patient provider relationship scale	x		x
ART adherence	x		x
WHO VAW (intimate partner violence)	x		
Social impact scale (stigma)	x		
Availability of social support	x		
Life events (trauma)			x
Infant health			x
Child mobility			x
Acceptability of CareConekta			x
Impact of COVID-19 & lockdown of HIV care and mobility			x
Laboratory tests			
HIV viral load*			x
Record review			
Antenatal and obstetric information	x	x	x
ART pharmacy records	x	x	x
Maternal laboratory results	x	x	x
Child HIV testing		x	x

* If no routine viral load result found in the three months before the study visit

DATA COLLECTION AND STORAGE

Data collection methods

Data will be collected in three ways:

- Face-to-face enrollment and follow-up questionnaires

- Medical record review (electronic and paper file records) to determine participant engagement in HIV care
- Electronic app usage and mobility data

Questionnaire data

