For a more detailed assessment of mobility, we will use ArcMap to geographically place all locations in which participants were recorded during the study period. We will plot origin and destination locations on a map of South Africa, and neighboring countries (if necessary). We will connect origin and destination locations using ArcMap's XY-to-line tool, and will use a spherical calculator to estimate the distance between origin and destination. The geographic data will be used in conjunction with the novel metrics of mobility developed by [name], which are reflective of the complex forms of mobility in sub-Saharan Africa. For example, we will apply geopolitical boundaries to location codes so that measures of internal migration and localized mobility within and across those boundaries can be estimated, such as inter- and intra-provincial mobility. We also will map mobility flow according to origin and destination pairs, classified by geopolitical categories. We will thereby demonstrate how geographic data can be used to characterize the mobility of populations – providing a vital alternative to survey measures – in order to measure the impacts of that mobility on care cascade outcomes, with broad applicability to the measurement of its impact on other health outcomes. We also will conduct a secondary analysis to validate whether self-reported anticipated travel matches data collected from the CareConekta app.

Aim 1b. To assess the association between mobility and engagement in HIV care for mother (retention in care and viral suppression six months after delivery) and infant (completion of routine early infant diagnosis).

Outcome: Impact of mobility on engagement in HIV care in the absence of the intervention
We will limit the analysis to the control arm only to explore the impact of mobility on engagement in HIV care in the absence of intervention. We will report baseline participant characteristics as collected on the questionnaire. We will report proportions and 95% confidence intervals for categorical variables and medians and interquartile ranges for continuous variables. Open-ended questions will be reviewed for key themes. Themes will be abstracted and quantified.

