To assess engagement in HIV care, we will report retention in care, which will be assessed at the six-month postpartum point and defined as no documented HIV-specific contact with any healthcare facility (including medication pick-ups) for >3 months. We also will report viral suppression six months after delivery, using thresholds of ≤ 50 and ≤ 1000 copies/ml. Additionally, we will report vertical HIV transmission and completion of the routine 10-week infant PCR test.

We will fit a series of models of mobility metrics on outcomes. For one, we will use a dichotomous exposure of mobility (any travel >50 km: yes/no), we will use Cox proportional hazard regression models to estimate the association of mobility on these outcomes, and will produce adjusted hazard ratios and 95% confidence intervals for retention in care and achieving viral suppression. We also will identify other predictors of engagement in HIV care. We will produce crude Kaplan-Meier curves to time to loss to follow-up and time to viral suppression by mobility group. Additionally, we will perform sensitivity analyses to explore how the estimated effect size changes when using varying cut-off points to define mobility.

Aim 2a. To assess the acceptability and feasibility of the standard and enhanced app, with a focus on identifying user preference and implementation outcomes.

Outcome: Acceptability and feasibility of CareConekta

Acceptability and feasibility data will be collected among all 200 participants. Those in the intervention arm will receive additional questions related to the enhanced app features. The outcomes selected for analysis in Aim 3a correspond with the Technology Acceptance Model for Resource-Limited Settings (TAM-RLS) framework, which was designed to draw attention to end-user acceptability as a predictor of mHealth technology adoption in low-resource settings.⁴⁶ We will report proportions and 95% confidence intervals for categorical variables and medians and interquartile ranges for continuous variables. For open-ended questions, we will create a list of categorical themes that emerge over multiple readings and calculate the proportions for the response categories. We will select key illustrative quotes for each theme.

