Aim 2b. To evaluate the initial efficacy of the enhanced CareConekta intervention, using notifications and staff contact to improve engagement in HIV care, by assessing the association between study arm and engagement in HIV care at six-months postpartum.

Outcome: Efficacy of the intervention

The overall efficacy analysis will include participants in both arms (n=200). To assess overall cohort engagement in HIV care, we will report retention in care, which will be assessed at the six-month postpartum point and defined as no documented HIV-specific contact with any healthcare facility (including medication pick-ups) for >3 months. We also will report viral suppression six months after delivery based on the viral load test closest to the six-month period, using thresholds of ≤50 and ≤1000 copies/ml. Additionally, we will report vertical HIV transmission and completion of the routine 10-week infant PCR test.

Study arm assignment is the primary exposure of interest. We will use Cox proportional hazard regression models to estimate the association of study arm assignment on these outcomes, and will produce adjusted hazard ratios and 95% confidence intervals for retention in care and achieving viral suppression by study arm. We also will identify other predictors of engagement in HIV care. We will produce crude Kaplan-Meier curves to time to loss to follow-up and time to viral suppression by study arm. In a secondary analysis, we will perform an as-treated analysis using self-reported data regarding actually reading the notifications and/or WhatsApp messages or staff phone calls to analyze the effect of receiving the intervention.

HUMAN SUBJECTS' PROTECTION

Ethical review process

The research protocol will be reviewed by the Institutional Review Boards at Vanderbilt University; the University of California, San Francisco; and the University of Cape Town in South Africa. All research activities will occur in South Africa. All procedures will conform to U.S. and South African ethical standards for human subjects' research.

Informed consent

Informed consent will be obtained for all participants as described in the "Informed Consent" section above.

Privacy and confidentiality

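### Aim 1b defines viral suppression as a six-month status but names only a time-to-suppression comparison, so the hazard ratio can pick up when women were tested

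*Combined protocol and SAP*

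**What the plan says.** All references are to the combined protocol and SAP.

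- **Outcome, Aim 1b** (Analysis Plan and Study Outcomes): "We also will report viral suppression six months after delivery, using thresholds of" 50 or fewer and 1000 or fewer copies/ml. No rule says which test supplies the status.
- **Outcome, Aim 2b**: "viral suppression six months after delivery based on the viral load test closest to the six-month period", at the same two thresholds.
- **Comparison, Aim 1b**: Cox regression that "will produce adjusted hazard ratios and 95% confidence intervals for retention in care and achieving viral suppression", with "crude Kaplan-Meier curves to time to loss to follow-up and time to viral suppression by mobility group". Cox is the only model named.
- **Comparison, Aim 2b**: Cox again, giving "hazard ratios and 95% confidence intervals for retention in care and achieving viral suppression by study arm", with matching Kaplan-Meier curves.
- **Analysis set, Aim 1b**: "We will limit the analysis to the control arm only to explore the impact of mobility on engagement in HIV care".
- **Which test can count** (Viral load testing and potential blood draw): a study sample is taken "If the participant has had no viral load test within 3 months prior to the six-month study follow-up visit". Otherwise the routine result stands.
- **Eligibility** (Inclusion and Exclusion Criteria): there is no viral load criterion, so women may already be suppressed when they enter.

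**The concern.** The outcome is a yes/no status at one point in time, while the comparison is of the speed of reaching it. A woman's suppression is seen only when she is tested. The look-back rule accepts a routine test from the three months before the visit, or a draw at the visit. Two women with the same six-month status can therefore carry event times about three months apart.

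This matters most in Aim 1b. The exposure there is mobility, which the Introduction itself describes as a possible barrier to engagement in care. If travel delays testing, a difference in test dates could be reported as a difference in suppression. The plan does not say where the clock starts, which test date is the event, when unsuppressed women are censored, or how women already suppressed at entry, or who later rebound, are treated. Two analysts could follow the text and obtain different hazard ratios from the same data.

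**Working it through.** The plan gives no power, event count or expected suppression level for this outcome, so there is no design figure to reproduce.

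**Inputs from the documents.** The control arm has 100 women and 25% are expected to travel long distances (Sample Size; Study arms). That gives 0.25 × 100 = 25 mobile and 75 non-mobile women in Aim 1b, if the travel figure applies to that arm and to the exposure used there.

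**Assumptions, not in the documents.** The clock starts at delivery. In each group 80% are suppressed and status does not change. Each woman has one routine postpartum test, uniform over months 0 to 6, and a study draw at month 6 if she has no test in months 3 to 6. A share of mobile women miss the routine test and are tested at month 6. The risk ratio is 1.00 by construction.

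**Why the hazard ratio moves.** With 25% of mobile women missing the routine test, the share with a suppression date before month 6 is:

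- first suppressed test: 0.8 × 0.75 = 0.60 mobile, against 0.80 non-mobile;
- closest test: 0.8 × 0.75 × 0.5 = 0.30 mobile, against 0.8 × 0.5 = 0.40 non-mobile. The 0.5 is the chance that a uniform test date falls in months 3 to 6.

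Yet 80% of each group is suppressed.

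**Size of the shift** (Cox model, Breslow ties, 200,000 simulated women per group, 25% missed):

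| Event date | Unsuppressed women censored at | Hazard ratio |
|---|---|---|
| Closest test | that test | 0.85 |
| Closest test | month 6 | 0.89 |
| First suppressed test | first test | 0.48 |
| First suppressed test | last test | 0.69 |
| First suppressed test | month 6 | 0.76 |

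The rows differ only in rules that the plan leaves open. With unsuppressed women censored at their last test, other missed shares give (closest test / first test): 5%, 0.97 / 0.93; 10%, 0.93 / 0.86; 50%, 0.73 / 0.47.

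**When the problem disappears.** If every woman is given the same follow-up time, all events are tied. With D events among n women in each group, the Breslow equation is D1 = (D0 + D1) × n1·HR / (n0 + n1·HR). Its solution is HR = (D1/n1) / (D0/n0), the risk ratio. For 15/25 against 60/75 this is 0.60/0.80 = 0.75. With test dates distributed alike in both groups and 80% suppressed in each, the hazard ratio is 1.00.

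**Noise at the trial's size.** With 25 against 75 women and 25% missed, the simulated 95% range is 0.59 to 1.24 for the closest test. For the first suppressed test with last-test censoring it is 0.42 to 1.15. Both include 1.

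**Aim 2b.** The added contact reaches only travellers, about 25% of an arm. Suppose 25% of control-arm travellers missed the routine test and no one in the intervention arm did. The missed share in the control arm would be 0.25 × 0.25 = 6.25%, between the 5% and 10% cases. The closest-test hazard ratio for intervention against control would then lie between 1/0.97 = 1.03 and 1/0.93 = 1.08.

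**The case against.** Several points on the other side stand.

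- Aim 1b announces several models and presents Cox as one of them, so a binary model is not ruled out. None is named, however, and the sentence on proportions with confidence intervals follows baseline characteristics and specifies no group comparison.
- A reader might infer that event times can only be test dates, so that the hazard ratio must be distorted. The documents do not support that. A single fixed follow-up time is not excluded, and it would return the risk ratio. The Kaplan-Meier wording points away from that reading but does not forbid it.
- A reader might also infer that tests done while travelling are lost. They are not: "Laboratory records, including viral loads, from any South African facility will be abstracted from the NHLS database". That protects the results but does not equalise test dates.
- The only test-selection rule written down is the closest-test rule, in Aim 2b. Under it the illustrated shift is modest. The larger figures need the first-test reading.
- The illustration assumes that women who miss routine testing attend the month-6 draw. File review activities plans for women who do not return. Their status may be missing, and no choice of model cures that.
- Aim 1b is framed as exploratory, Sample Size disclaims power for Aim 2b, and six-month suppression will be reported whichever model is used.

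These points limit the harm. They do not supply the missing comparison.

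**Conclusion.** The point holds as a mismatch between outcome and analysis, mainly in Aim 1b. The plan defines a six-month status, names no between-group comparison of it, and leaves open the rules that the named model needs. Run on test dates, that model can show a difference where status is identical.

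That conclusion rests on the text. The sizes rest on assumed suppression levels, test dates and missed-test shares, because the documents give none. On those assumptions, with 25% missed, the hazard ratio is 0.85 to 0.89 by closest test and 0.48 to 0.76 by first suppressed test, against a risk ratio of 1.00. At about 25 against 75 women, a single trial could not separate a shift to 0.85 or 0.69 from noise. That statement does not extend to the most extreme rule (0.48).

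It would go too far to say that the trial's hazard ratio will be biased by a known amount or in a known direction, or that Aim 2b is seriously affected. With equal timing the closest-test hazard ratio is close to the risk ratio, and little effect is expected in Aim 2b. The point should be fixed because the pilot's estimates are meant to inform later sample sizes, and a six-month risk comparison serves that purpose directly.

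**What to change.** In Aims 1b and 2b, compare six-month suppression (≤50 and ≤1000 copies/ml) by mobility group or arm as a binary outcome. Report the risk difference and risk ratio with 95% confidence intervals, for example by modified Poisson regression with robust variance. Apply the Aim 2b closest-test rule in both aims, restricted to postpartum tests.

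Keep Cox and Kaplan-Meier for time to loss to follow-up. If time to suppression is kept, make it secondary and state its origin, event date, censoring rule and risk set. Show the number of women without a qualifying test in each group.

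The cost is SAP wording and a different regression call, with no change to sample size or data collection. Women without a qualifying test have missing status, and a result up to three months old can still miss a later rebound. Precision stays low. At 80% suppressed, the 95% half-width in Aim 1b is 1.96 × √(0.16/25 + 0.16/75) = 0.181, about ±18 points. In Aim 2b it is 1.96 × √(0.16/100 + 0.16/100) = 0.111, about ±11 points. Both comparisons remain descriptive.

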	Q1	Q2	Q3	Q4	Q1	Q2	Q3	Q4	Q1	Q2	Q3	Q4
Study preparation												
IRB approval and renewal												
ClinicalTrials.gov registration												
Develop study instruments and REDCap database												
Adapt CareConekta smartphone app												
Confirm eligibility, recruit and consent participants												
Enrollment questionnaire												
Participant follow-up												
Follow-up questionnaire												
File review												
Data analysis												
Manuscript preparation												
R01 submission and revision												

STUDY DESIGN

Sample Size

We will enroll 200 participants.

For this pilot trial formal sample size estimation was not conducted. The sample size was reached based on the feasible enrolment from the study site within the study timeline. Approximately 4,000 women seek antenatal care at the MOU annually; ~30% of these are HIV-positive, about 1 200 per year, or 100 per month. Our formative work (HREC REF 792/2016 and 227/2017) showed that over half of these women own smartphones. If we conservatively estimate that 30% of all pregnant, HIV-positive women seeking antenatal care each month will be eligible and interested which equals 30 participants enrolled per month. We anticipate that it will take approximately seven months to reach our enrolment target of 200 participants (see Timeline above).

Based on our earlier work in South Africa and at the study site, we estimate that 25% of the participants will engage in long-distance travel during the study period. A sample size of 200 allows us to characterize the mobility experiences of 50 women who travel and explore differences with those who do not. While we do not anticipate having sufficient power to detect statistically significant differences between groups in Aims 2b, the information gained through this pilot study will inform sample sizes for larger future studies should this pilot show promise.

Study arms

- **Control arm (n=100):** Participants will receive standard CareConekta, which will track their mobility and allow the participant to look up new ART facilities upon request.
- **Intervention arm (n=100):** Participants will receive standard CareConekta with the following additions:
 - text notifications of nearby ART facilities when they have traveled >50 km from the study site for >7 days

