After the informed consent is signed, the participant will be assigned a study ID number. The master list of study ID numbers linked with participants' names and MOU clinic file numbers will be kept in a password-protected file, accessible only by designated study staff. In order to re-contact the participant and access her medical records, we will collect identifying information on a separate paper-based linkage form, including contact information, name, study number, clinic record number, phone number, national identification number, address, date of birth, and we will also update this form with infant information, when available. As is standard practice for research studies at the study site, the participant may also provide details for an alternative contact person in the event that we are unable to reach the participant after multiple attempts. No details about the participant will be shared with the alternative contact; study staff simply will ask that the participant return to the clinic when she can. Identifiers and study details will only be linked on the linkage form which will be stored in a locked cabinet in the study office.

Randomization

Randomization will occur after study ID assignment and will follow a dynamic permuted block design. All participants will be randomized 1:1 to the control or intervention arms. Randomization numbers will be generated prior to the start of the study, and placed in sequentially numbered opaque envelopes. Randomization envelopes will be stored in a locked cabinet in the study office at the study site that will be accessed by the study coordinator when a participant is fully consented, with independent documentation of the participant ID number, randomization date, and randomization assignment.

Enrollment questionnaire

Following randomization, study staff will complete a face-to-face questionnaire with each participant. Responses will be recorded directly into a password-protected REDCap database by an interviewer using a tablet computer or laptop. The questionnaire will collect information on demographic characteristics, smartphone type and usage preferences, barriers and facilitators to engagement in HIV care, and travel intentions. Response options primarily will be categorical, with open-ended questions to allow for deeper elaboration. Questionnaire data collected will identify participant responses by study ID, not by names or identifiable data.

App installation

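### The whole-arm Aim 2b contrast is valid but is expected to be diluted about four-fold, and no comparison of the randomised arms is planned among women who reach the travel trigger

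*Combined protocol and SAP*

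**What the plan says.** **What differs between arms.** Under Study arms, both groups of 100 get standard CareConekta. The intervention group also gets "text notifications of nearby ART facilities when they have traveled >50 km from the study site for >7 days", plus staff calls or WhatsApp messages at the same threshold. The interim procedures for the intervention arm repeat this. Other app notifications may go to either arm and are unrelated to linkage to care.

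**How many are expected to travel.** Under Sample Size: "we estimate that 25% of the participants will engage in long-distance travel during the study period". The same section adds: "A sample size of 200 allows us to characterize the mobility experiences of 50 women who travel". It does not define long-distance travel there as the 50 km / 7 day trigger.

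**Analysis.** Under Aim 2b: "The overall efficacy analysis will include participants in both arms (n=200"). Assigned arm is the primary exposure, analysed with Cox models. A secondary as-treated analysis uses self-report of having read the messages or of staff calls. Aim 1b relates mobility to outcome, but in the control arm only.

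**Use of the result.** Sample Size concedes low power for Aim 2b and says that "the information gained through this pilot study will inform sample sizes for larger future studies should this pilot show promise". Dilution is not mentioned.

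**The concern.** A woman who never reaches the trigger receives, by design, the same app and the same contact whichever arm she is in. On the plan's own travel estimate that describes about three quarters of each arm. The whole-arm estimate therefore averages whatever happens in triggered women with an expected zero in everyone else.

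The section on potential benefits locates the benefit in intervention women who are notified while travelling, yet no planned analysis estimates the randomised effect in them. The as-treated analysis does not fill the gap. Only intervention women who triggered can count as treated, and the untreated group mixes non-travellers with travellers who did not read the messages. It therefore compares travellers largely with non-travellers.

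At stake is how the pilot is read. A worthwhile effect in travelling women could appear as a hazard ratio near one. The whole-arm figure also depends on this site's travel share, whereas the Abstract looks ahead to a larger trial in different geographic settings, where the share may differ.

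**Working it through.** **Inputs from the protocol.** 200 women, randomised 1:1, 100 per arm; 25% expected to travel (Sample Size). For sensitivity only: 44% planned travel at Johannesburg sites (Introduction). Loss figures in the Introduction: 25.2% at one year among women pregnant at ART initiation, and 47.9% within six months of delivery in a Johannesburg cohort.

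**Assumptions.** The 25% applies to the trigger. There is no effect in untriggered women. Two-sided alpha is 0.05 (the plan gives only 95% intervals). Six-month retention is 75% in non-travellers and 52% in control travellers; these echo the loss figures above, which are not rates by travel status. The gains of 20 and 10 points have no source in the documents.

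**1. The plan's own figure.** 0.25 × 200 = 50 travellers, as stated. Per arm: 0.25 × 100 = 25 triggered, 75 not.

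**2. Risk difference.** RD(whole arm) = f × RD(triggered), where f is the share triggered. At f = 0.25 the shrinkage is 1/0.25 = 4.0-fold. At f = 0.44 it is 1/0.44 = 2.3-fold. At f = 0.15 it would be 1/0.15 = 6.7-fold.

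**3. Hazard ratio, the planned measure.** Approximate HR = ln(1 − p_int) / ln(1 − p_ctl), with p the risk of loss.
- Loss 25.2% in everyone, halved in intervention travellers. Travellers: ln(0.874)/ln(0.748) = 0.46. Whole arm: intervention risk 0.75 × 0.252 + 0.25 × 0.126 = 0.2205, so HR = ln(0.7795)/ln(0.748) = 0.86. Ratio of log HRs: 5.0.
- Travellers at twice that loss (50.4%, halved to 25.2%). Travellers: HR 0.41. Whole arm: 31.5% v 25.2%, HR 0.77. Ratio of log HRs: 3.3.
- Non-traveller loss of 15% (assumed), 25.2% or 47.9%, with traveller loss 1 to 2 times that (capped at 95%): ratio 3.2 to 5.1 at 25% travel and about 2.0 to 2.8 at 44%.

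**4. Precision.** SE = √[p₁(1 − p₁)/n + p₀(1 − p₀)/n]. Half-width = 1.96 × SE. Power = Φ(d/SE − 1.96) + Φ(−d/SE − 1.96). Chance of the wrong sign = Φ(−d/SE).
- Whole-arm control retention: 0.75 × 0.75 + 0.25 × 0.52 = 0.6925.
- Whole-arm intervention retention, 20-point gain: 0.75 × 0.75 + 0.25 × 0.72 = 0.7425.
- Whole-arm intervention retention, 10-point gain: 0.75 × 0.75 + 0.25 × 0.62 = 0.7175.

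| Gain in triggered women | Comparison | Difference | SE | Half-width | Power | Wrong sign |
|---|---|---|---|---|---|---|
| 20 points | Whole arms, 100 v 100 | 5.0 points | 0.0636 | 12.5 points | 12% | 22% |
| 20 points | Triggered, 25 v 25 | 20 points | 0.134 | 26 points | 32% | 7% |
| 10 points | Whole arms, 100 v 100 | 2.5 points | 0.0645 | 12.6 points | 7% | 35% |
| 10 points | Triggered, 25 v 25 | 10 points | 0.139 | 27 points | 11% | 24% |

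**5. Later trial at 80% power, 20-point case.** n per arm = (1.96 + 0.84)² × [p₁(1 − p₁) + p₀(1 − p₀)] / d². Whole arm: about 1,269 per arm, or about 2,540 women. Triggered women: about 89 per arm, so 178/0.25 = 712, about 710 enrolled. Each figure is right for its own question.

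**The case against.** **The whole-arm contrast is not an error.** It answers Aim 2b as worded, the association of study arm with engagement, and randomisation protects it. A reader might infer that it is biased or should be replaced. The documents do not support that. For a later all-comer trial analysed by arm with a similar travel share, about 2,540 is the right order of size under these assumptions, not an inflated one.

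**The plan does not name the whole-arm hazard ratio as its sizing input.** A reader might infer this, or a go/no-go rule, from the Sample Size text. That text refers only to information gained and to the pilot showing promise. Acceptability and feasibility are part of the primary objective. Aim 1a will report the share meeting 50 km for 7 days, and Aim 1b will report control-arm outcomes by mobility, although its dichotomous exposure is any travel over 50 km, with other cut-offs as sensitivity analyses. Some of the useful inputs are therefore already planned.

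**A triggered subset has weaknesses of its own.** These objections stand:
- It is defined after randomisation. First crossing precedes arm-specific contact, but participants know their arm, the app is installed after randomisation, and a raffle was offered to keep it installed with GPS on. App retention could differ by arm.
- Outcome capture is weakest there. Visit and pharmacy data cover Western Cape public facilities only (File review activities), while the Study Site section describes travel to the Eastern Cape. Successful linkage there could look like loss. National laboratory records and self-reported clinic switching only partly help.
- Some women will trigger after the 10-week infant test, after suppression, or too late for a gap of more than three months to accrue.
- The 26-point half-width exceeds the assumed 20-point effect.

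They rule out making this subset the principal estimate. They do not rule out reporting it.

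**Low power is openly admitted.** That is so, and it is not the point here. Dilution is a separate matter and is not mentioned.

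**Conclusion.** The point holds as a cheap improvement, not as a flaw in the main analysis. On the plan's 25%, the whole-arm risk difference is expected to be one quarter of the effect in triggered women. Four-fold is exact only for a risk difference with no effect in untriggered women; for the log hazard ratio it is roughly 3- to 5-fold, and about 2- to 3-fold if 44% travel.

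The gap is that no planned analysis compares the randomised arms among triggered women, so the whole-arm result would stand alone and could mislead if used to judge promise or to size a later trial.

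The power figures are illustrations. Travellers' retention and the size of the gain are assumed, and at a 10-point gain the triggered contrast helps little. A reader might also infer that three quarters of the intervention arm can never receive the intervention. That is an expectation resting on the 25%, which the protocol does not tie to the trigger.

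One related passage needs reconciling: About CareConekta describes the automatic facility notification without limiting it to one arm, whereas Study arms and the interim procedures limit it to the intervention arm.

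**What to change.** **Aim 2b.** Keep the whole-arm contrast as the main analysis, described as the effect of offering the enhanced app. Add a pre-specified supporting, descriptive comparison of the randomised arms among women in either arm whose app record first meets more than 50 km for more than 7 days, with follow-up from that first trigger. For it:
- report by arm the number triggered, app transmission and baseline balance;
- restrict each outcome to women who could still have it after the trigger;
- give estimates with intervals, and note that visit and pharmacy data cover the Western Cape only.

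**Sample Size.** State that the whole-arm risk difference is expected to be about one quarter of the effect in triggered women if 25% trigger. State also that later sample sizes will consider the trigger proportion and the control-arm outcome rate in triggered women as well as the whole-arm estimate.

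**Cost.** Some wording and one extra analysis on data already collected in both arms. The result will be imprecise (about 25 v 25 women, half-width about 26 points), women whose app stops transmitting may be missed, and selection is possible if app retention differs by arm.
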